### **1.8 Number of Subjects required**

Main hypothesis: Investigators postulate that the group of participants supervised by a psychologist via teleconsultations will have an average weekly number of connections at least twice as high as that measured in the total autonomy group.

Secondary hypothesis: Participants who use the solution should have a lower frequency of lexicon access disorders than participants who do not use it. This study should make it possible to assess its extent and discuss its clinical relevance.

To test these hypotheses, 3 groups of participants will be constituted:

- 1 group "application supervised by a psychologist via teleconsultations" (n=30)

- 1 group "application in total autonomy" (n=30)  
- 1 "control" group without using the application (n=30).  
A 4th group of "healthy controls" (n=70) will also be needed to calculate the "reliable change index" (an index that evaluates the potential learning effect when a cognitive test is performed twice over a period of less than one year). The larger size of the latter group is justified by the expected higher number of people lost to follow-up on the second visit.

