### 1.9 Description / Subject Recruitment Methods

Healthy controls will be matched to participants on age (+/-5 years) and socio-educational level (+/-2 years of study).

All subjects will be seen during a consultation.

Participants will be recruited through their neurologist or neuropsychologist during a consultation as part of their usual follow-up.

Healthy controls will be recruited through posters in the neurology department University Hospitals, and in the practices of private neurologists

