**1.14 Search process**

**I. PATIENT COURSE :**

Inclusion visit as part of the usual follow-up:

- Participants and subjects will be informed of the study by an investigator during a consultation at their respective centers.

- A neuropsychologist will carry out the consultations

- After verification of the eligibility criteria by the investigator and presentation of the objectives of the study, an information document will then be given to the patient for an attentive reading.

- After a reflection period, if the patient agrees to participate in the research and has not objected to the use of these data in this research, then randomization will be carried out via an online module (CleanWeb). This individual randomization will be done according to a 1:1 ratio with stratification by age (+/-5 years) and socio-educational level (+/- 2 years of study) and a randomization block of 4.

- The neuropsychological assessment (V1) will be carried out by the psychologist: it consists of questionnaires and cognitive exercises lasting one and a half hours (the cognitive functions tested are listed in paragraph 1.8).

- The characteristics of each patient's epilepsy will be collected from his or her computerized medical record.

Depending on the group obtained by randomization (A/ B / C), the psychologist will present the application to the patient or not, and will inform him or her whether or not he or she will have telephone appointments.

At the end of visit 1, participants will be invited to use the digital application at their convenience for the autonomous group (B). Participants in the teleconsultation group (A) will be called once a week for 16 weeks to follow up on their connection to the application and to check that they do not present any particular difficulties in using it. A link will be provided to download the application. It will be sent to the patient on paper at the end of the visit.

The duration of use of the digital application will be 4 months.

Group C participants do not use the digital application.

➤ **Follow-up visit (V2) = 5 months post-inclusion (research specific)**

During this visit, participants in group A, B or C will undergo a neuropsychological assessment. The patient in group A or B will provide to the psychologist his or her number of connections to the application.

The patient in group A or B will also answer an interview on how he or she feels about using the application.

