### Data Entry

Once documented and validated by the Investigator, the pages of the Observation Notebook of the different centers are sent to the Nancy University Hospital, to be entered into the database.

An Excel file will be created by the investigator and will be strictly located on the server of the university hospital. The pseudonymized data will be collected and entered in this file by the investigator. This file will then be transmitted for statistical analysis to the UMDS in a secured way via USB key protected by a password.

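### The protocol of an open trial prints one fixed block size, so anyone who follows most allocations in a stratum could foresee part of the sequence: a minor weakness, cheaply removed

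*Protocol*

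**What the plan says.** Protocol section 1.14 (patient course, inclusion visit) has patients randomized in an online module, CleanWeb, after eligibility has been checked, information given and agreement obtained. On the ratio it says: "This individual randomization will be done according to a 1:1 ratio". Strata are formed by age and educational level; centre is not a stratum, and the number of strata is not given. The sentence ends "and a randomization block of 4". No passage varies the block size or keeps it from recruiting staff.

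There are three randomized arms. Section 1.8 says "To test these hypotheses, 3 groups of participants will be constituted", with 30 patients each.

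The allocation is open once made. Section 1.14: "Depending on the group obtained by randomization (A/ B / C), the psychologist will present the application to the patient or not". Section 1.9 gives the recruiters: "Participants will be recruited through their neurologist or neuropsychologist during a consultation as part of their usual follow-up". Under section 1.15 the subject code carries the centre number, the inclusion order number and the arm letter. Section 1.17 (Data Entry) sends notebook pages from all centres to the coordinating hospital and adds: "The pseudonymized data will be collected and entered in this file by the investigator".

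The primary endpoint (section 1.5) is the weekly number of connections, compared between supervised arm A and autonomous arm B.

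**The concern.** An online module conceals each single assignment until it is released. It does not stop inference from past assignments. Once the block length is known and constant, the last places in a block can be deduced by anyone who has seen the earlier ones, before deciding whether or when to offer the trial to the next patient.

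This matters more than usual here because the endpoint is a usage behaviour. It plausibly depends on motivation, which a clinician can judge in a consultation and which is not among the baseline data listed in section 1.16. If keener patients entered when A was due and less keen ones when B was due, the A versus B difference would contain selection that the adjustment planned in section 1.19 could not directly remove.

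The weakness is separate from whether 4 suits three arms. A printed, constant 3 or 6 would share it.

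**Working it through.** The protocol gives no predictability or power figure to reproduce.

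**Inputs.** Three arms of 30, 90 patients (1.8); one block size of 4 (1.14); four centres, named for the normal controls (1.14); centre not a stratum (1.14). Assumptions: the fraction *p* of a stratum's allocations that a recruiter sees, and, where bias is computed, the strength of steering.

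**Block of 4 and three arms.** 4/3 is not a whole number and 90/4 = 22.5. If one arm were always doubled (AABC), 22 complete blocks would give 44/22/22. The make-up of the block is therefore undefined, and two versions are shown below.

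**Certain assignments, full visibility (p = 1).** An assignment is certain when all remaining places in the block belong to one arm.
- Block of 3 (ABC): only the third place is certain. 1/3 = 33.3%.
- Block of 6 (AABBCC): the sixth always; the fifth if the last two match, probability 1/5. (1 + 1/5)/6 = 20.0%.
- Block of 4, AABC known: the fourth always; the third if the last two are both A, probability 1/6. (1 + 1/6)/4 = 29.2%.
- Block of 4, doubled arm unknown: the fourth only if the first three already contain a repeat, probability 1/2. (1/2)/4 = 12.5%.

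Correct-guess rates are 61.1%, 56.1%, 64.6% and 50.0%, against 33.3% by chance. With AABC, 90 patients and 1 to 16 strata, unfinished blocks lower the certain share from about 29% to 22%.

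**Partial visibility.** Count an assignment as certain only if every earlier one in its block was seen, each independently with probability *p*:
- ABC: p²/3
- AABBCC: (p⁵ + p⁴/5)/6
- AABC: (p³ + p²/6)/4
- doubled arm unknown: p³/8

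| Block | p = 1 | p = 70/90 | p = 1/4 |
|---|---|---|---|
| 3 | 33.3% | 20.2% | 2.1% |
| 6 | 20.0% | 6.0% | 0.03% |
| 4 (AABC) | 29.2% | 14.3% | 0.65% |
| 4 (doubled arm unknown) | 12.5% | 5.9% | 0.2% |

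The column p = 1/4 stands for four equal centres, each seeing only its own patients. The column p = 70/90 assumes that one team sees everyone except the 20 participants budgeted at a private office in section 1.21.

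**Effect on A versus B.** Assume no true effect, full visibility, and patients 0.5 SD more willing when A is likelier next than when B is (+0.25 against -0.25). Simulation (1,500 trials, 90 patients, one stratum) gives an A-B bias of 0.25 SD for a fixed block of 3 and 0.21 SD for 6, with the 5% t-test rejecting in 15% and 13% of trials. A normal approximation with 30 per arm agrees: the shift in the test statistic is 0.21/√(2/30) = 0.81, and P(Z > 1.96 - 0.81) + P(Z < -1.96 - 0.81) ≈ 0.125 + 0.003 ≈ 13%. With four equal centres, each guessing from its own counts, the bias is 0.02 to 0.06 SD. At 0.06 the shift is 0.23 and rejection about 5.6%, close to nominal.

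**The case against.** The strongest counter-argument is that nobody may see enough. Patients are informed at their respective centres, four centres are named, neurologists recruit as well as neuropsychologists, and centre is not a stratum, so patients from other sites interleave within each block. If the four centres are equal, the problem nearly vanishes and varying the block size changes nothing measurable. This stands, and it limits the severity.

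It does not remove the point, because the documents leave a dominant site open. Section 1.21 budgets set-up of one external centre and travel to a private office for 20 participants, and section 1.14 refers to the study's neuropsychologist in the singular.

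A reader might infer more than the documents support:
- **That the recruiting psychologist learns every allocation.** Only the arms of the patients that he or she sees are documented.
- **That central data entry reveals the sequence in time.** Section 1.17 has pages sent after validation, with no statement that this happens as patients enter.
- **That a third of assignments are certain and 70.8% can be guessed with the printed block.** Those figures belong to a two-arm AABB block, which is not this design.
- **That eligibility is not settled before the arm is released.** Section 1.14 already places eligibility, information and agreement before randomization.

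**Conclusion.** The point holds as a minor design weakness. One fixed block size is disclosed in an open trial whose recruiters include people who learn the arms of the patients they see. With three arms, the foreseeable share runs from 12.5% to 33% under full visibility down to below 1% for a block of 4 (about 2% for a block of 3) if four equal centres see only their own patients. The documents do not say where in that range the trial lies.

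A reader might conclude that patients will be steered, or that the A versus B test is invalid. The documents show neither. The false-rejection rate of about 12-15% is an upper case: it needs one person who sees a whole stratum and an assumed 0.5 SD steering effect that no passage supplies. The mismatch between a block of 4 and three equal arms, in the same sentence, is the firmer error.

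**What to change.** In section 1.14, delete "and a randomization block of 4" and state that allocation uses permuted blocks of randomly varying size, in multiples of the three arms, set in CleanWeb by the methodology unit and not disclosed to investigators or psychologists. Make this edit together with the one that reconciles the block of 4 with three equal arms. No extra sentence on the order of eligibility and agreement is needed.

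The cost is one sentence and a setting in a module already budgeted in section 1.21. The downside is a slightly larger possible imbalance: an unfinished block of 9 can leave two arms up to 3 apart in a stratum, against 2 for a block of 6 and 1 for a block of 3.

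The gain is partial. With undisclosed blocks of 6 and 9, no assignment is certain. In the upper case above, a recruiter who still bets on the least-used arm guesses 54% correctly, and the bias falls to about 0.18 SD, from 0.21 (fixed 6) or 0.25 (fixed 3).

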**I. NORMAL CONTROL COURSE :**

➤ **Inclusion visit (research specific)**

Normal controls are recruited through posters and on a voluntary basis in the 4 centers. They are therefore in contact (telephone or e-mail) with the neuropsychologist of the study on their own initiative. The objectives of the study are then presented during this contact. If the subject gives his agreement, an appointment is fixed in order to carry out the inclusion visit. On the day of the visit, the subject is given an information document that he or she should take the time to read. After a period of reflection, if he agrees to participate in this research and if he does not object to the use of his data within the framework of this research, the acts specific to the research may be carried out (neuropsychological assessment including only cognitive data + collection of clinical characteristics).

➤ **Follow up visit : 5 months post inclusion (research specific)**

During this visit, the normal control will undergo the same neuropsychological assessment as in visit V1 with the neuropsychologist.

**1.15 Modality of de-identification of subjects**

Check the appropriate box(es) :

by a serial number assigned to the inclusion

other identification mode, specify: a number for the number of the center  
- the order number assigned to the inclusion - A letter for the identification Patient (C) versus Witness (T) - subject initials (first letter of the surname and first name) + a letter for randomization (A: application group + teleconsultation), (B: autonomous application group), (C: control group)

The correspondence table that links the patient's identity to his or her inclusion number will be kept in the investigator binder stored with the CRFs in the locked cabinet in box 5 of the Neurology Department.

**1.16 Nature of the data collected and processed**

The data are collected specifically and prospectively on a written observation notebook.

**For participants, the data collected for research are:**

Data present in the medical record:

- patient demographics: gender, age, years of study after graduation, manual laterality, work activity and family situation

- clinical data: characteristics of epilepsy: age of onset, number of seizures, current drug therapy, type of epilepsy.

And neuropsychological assessment data:

- Questionnaires on self-esteem, mood, anxiety and feelings about the frequency of language difficulties.
- computerized (5 in total) and paper-and-pencil (3 in total) tests to measure language, attention and executive abilities.

**Digital solution data:**

At the end of the second visit, the patient will download a statistical file containing the number and time of connection to the digital solution. This file will be transmitted by the patient to the investigator in a secure way (via USB on a protected file).

**No private data will be collected via the digital solution.**

During the second visit, the patient will be asked questions on how he or she feels about using the digital solution and the answers will be directly reported in the observation notebook.

**For healthy controls, the data collected for research are:**

- demographic data: sex, age, number of years of study after high school graduation, manual laterality, professional activity and family situation.
- Inclusion and follow-up neuropsychological assessment data consisting of computerized (5 in total) and paper-and-pencil (3 in total) tests to measure language, attentional and executive abilities.

## 1.17 Flow of personal data and procedures for ensuring their confidentiality

### Data Collection

During the course of the research, the Investigator, or any person designated in writing, will record, for each person included in the research, an observation notebook in paper format specific to the research from the source data.

The Investigator is responsible for the quality, accuracy and relevance of the data collected in the Observation Notebook, the data collection form.

### Data Entry

Once documented and validated by the Investigator, the pages of the Observation Notebook of the different centers are sent to the Nancy University Hospital, to be entered into the database.

An Excel file will be created by the investigator and will be strictly located on the server of the university hospital. The pseudonymized data will be collected and entered in this file by the investigator. This file will then be transmitted for statistical analysis to the UMDS in a secured way via USB key protected by a password.

### Data Analysis

The statistical analyses will be carried out within the Data Management and Statistics Methodology Unit (UMDS)- DRCl.

In accordance with the third paragraph of Article 56 of the French Data Protection Act, the presentation of the results of data processing may under no circumstances allow the direct or indirect identification of the persons involved in the research.

## 1.18 Duration

Duration of subject participation: 5 months  
Length of inclusion period : 2 years  
Total research duration: 3 years

## 1.19 Statistical Analysis

Descriptive analysis: The parameters collected will be described in each group by percentages (categorical variables), mean +/- standard deviation, quartiles, and extreme values (continuous variables).

Main analysis: the comparison of the mean number of connections will first be carried out by a parametric (Student's t) mean comparison test or its non-parametric (Man-Withney) equivalent if the hypotheses of normality and equality of variances are not verified. In the case of significant

differences in one or more parameters between the 2 groups compared, these adjustment variables will be introduced into a linear regression model. A stepwise selection method is provided.

Secondary analysis: Before-after comparisons will be performed by tests on paired series, the Student's t-test when the variable to be compared is quantitative (or the Wilcoxon test), and Mac Nemar's Chi2 when the variable to be compared is qualitative.

The value of the "Reliable Change Index" will be obtained in the group of healthy controls by the product of the standard error of the score concerned and the standard deviation of the difference observed at 2 measurement times.

The significance threshold is set at 5%. An a posteriori power calculation is also planned.

The analyses will be performed by the UMDS, using SAS v9.4 software (SAS Institute Inc., Cary, NC, USA).

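### The primary A-versus-B comparison adjusts only for variables that happen to differ significantly between randomised arms, chosen stepwise, instead of for age and education fixed in advance

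*Protocol*

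**What the plan says.** Protocol section 1.19 (main analysis) compares the mean number of connections first by Student's t, or by the Mann-Whitney "equivalent if the hypotheses of normality and equality of variances are not verified". A second step follows where there are significant "differences in one or more parameters between the 2 groups compared, these adjustment variables will be introduced into a linear regression model". The text adds: "A stepwise selection method is provided".

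Section 1.14 randomises patients with "stratification by age (+/-5 years) and socio-educational level (+/- 2 years of study" as the stratification rule. Section 1.8 gives 30 patients per group and expects at least twice as many weekly connections under supervision.

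No section names a covariate for the primary analysis, says that the arm term stays in the stepwise model, limits the screened parameters to baseline variables, or says whether the unadjusted or the adjusted result is the primary one.

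**The concern.** Groups A and B are formed by randomisation, so any baseline difference between them is chance. Its p-value says nothing about whether the variable predicts connections, and prediction is the reason to adjust. A strongly prognostic but balanced variable is left out, while an irrelevant but imbalanced one becomes a candidate.

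The rule also works against the design. Age and education were important enough to stratify on, yet the better the stratification works, the less likely they are to be adjusted for. When the trigger fires there are two p-values for the only primary comparison, and the protocol does not rank them.

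**Working it through.** **1. Figures in the plan.** There is none to reproduce. The protocol gives no mean, SD, design power or covariate effect. Everything below rests on stated assumptions.

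**2. How often chance triggers adjustment.** Section 1.16 lists six demographic and four clinical variables: 10 in all, or 8 without age and years of study. For k independent tests, each of exactly 5% size, P(at least one significant) = 1 - 0.95^k.

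- k = 8: 1 - 0.95^8 = 0.337
- k = 10: 1 - 0.95^10 = 0.401

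The protocol does not say whether baseline test scores are screened too. Section 1.14 states "then randomization will be carried out via an online module (CleanWeb") and only afterwards lists the assessment: "The neuropsychological assessment (V1) will be carried out by the psychologist". If the 13 score items of section 1.7 count, k = 23 and the figure is 1 - 0.95^23 = 0.693. With the response times of the three naming tests, k = 26 and it is 1 - 0.95^26 = 0.736. None of these is a bound. Positively correlated variables would lower them, and so would Fisher's exact test on the categorical variables (true size about 1-2.6% at 30 per arm).

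**3. How often age or education gets in.** Without stratification: 1 - 0.95^2 = 0.0975. With stratification, simulation gives:

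- near-perfect balance assumed: under 0.1%
- four strata, blocks of 4: under 0.5%
- coarser multi-year cells: about 0.7-2%
- cells of 5 years by 2 years: about 4-5%. Many strata are then nearly empty (some 31-37 occupied for 60-90 patients, assuming an age SD of 13 years and an education SD of 2.5 years).

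The direction is the same throughout; the size depends on stratum width.

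**4. Size and power.** Simulation: 6,000 trials per setting, 30 per arm, normal outcome, 10 independent covariates of which only age and education are prognostic, four strata, blocks of 4 between the two arms compared, backward elimination at 5% with arm retained. The effect is d = (1.960 + 0.842) × sqrt(2/30) = 0.723, which gives 80% unadjusted power by normal approximation.

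| Variance explained by age and education (assumed) | Type I error, protocol rule | Type I error, fixed adjustment | Power, protocol rule | Power, fixed adjustment |
|---|---|---|---|---|
| 10% | 4.7% | 5.3% | 79% | 82% |
| 30% | 3.1% | 5.1% | 80% | 91% |
| 50% | 2.1% | 5.2% | 83% | 97% |

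The Monte Carlo standard error near 5% is sqrt(0.05 × 0.95 / 6000) = 0.3 points, so the first row is close to nominal either way. The unadjusted t-test alone had power of 79%, 80% and 84%, so the rule recovers none of what the stratification factors could give. Letting the stepwise step drop the arm term changed these rates little, but a model without that term estimates no effect.

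**5. Two p-values.** Simulated overdispersed counts: mean 32 in the autonomy group (2 per week × 16 weeks), coefficient of variation 0.5-1.0, 8-10 candidate variables, Shapiro-Wilk and F-tests at 5%, entry and stay at 0.15, all assumed. The unadjusted and adjusted results fell on opposite sides of 0.05 in 0-9% of all trials at a true ratio of 2, and in 3-10% at 1.5. With age and education explaining 20% of the variation, type I error of the final p-value was 2.5-3.9% with those two balanced and 4.5-5.3% without. If either p-value could be claimed, it was 2.9-4.4% and 5.8-6.7%.

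**The case against.** **The harm is modest.** True. At the protocol's own expected ratio of 2, the two results disagree in at most about 9% of trials, and in close to none when counts vary little. A ratio of 1.5 appears nowhere in the protocol.

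**A statistical analysis plan may settle it.** It could rank the two results, and section 1.19 does order the steps. But the trigger and the stepwise selection are written in the protocol, and a plan that followed it would inherit both.

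**The rates depend on unstated tests and strata.** This stands. The 34-40% assumes independent tests of exact 5% size, and the entry rate for age and education is a range, not one figure.

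**Nothing shows that age or education predicts connections.** Also true; the power gain is conditional on it. Fixing the covariates in advance still removes the dependence on chance imbalance, at a small price.

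**Stronger readings.** A reader might infer that the rule inflates the type I error. Under a fixed reading it does not: the simulated values are at or below nominal, and the modest excess (5.8-6.7%) needs both a free choice between p-values and no balance on the two factors. A reader might also infer that the named methods are invalid because section 1.8 states the effect as a ratio. A difference in means is a valid test of superiority, and section 1.4 asks only for a comparison. The scale of the estimate is a choice that an analysis plan may make.

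**Conclusion.** The point holds as a badly fixed rule for the primary analysis. Chance imbalance decides whether the comparison is adjusted and for what, in about 34-40% of trials if 8-10 independent variables are tested at 5%, and more if test scores are screened. The stratification factors are rarely admitted (under 0.1% to about 5% of simulated trials). Two p-values are left unranked.

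If age and education are prognostic, the cost is a test somewhat below nominal size and lost power: about 3, 11 and 14 points (82 - 79, 91 - 80, 97 - 83) at 10%, 30% and 50% of variance explained. Those shares, the normal outcome and the four strata are assumptions. If the two factors are not prognostic, this loss disappears and the unfixed model remains. The defect should be corrected; it does not invalidate the trial.

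**What to change.** In section 1.19, delete the significance trigger and the stepwise selection. In their place:

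- Name one primary A-versus-B model of the number of connections, with the arm term always retained and age and years of study as fixed covariates whether or not they differ between arms.
- Use a method suited to skewed counts, for example linear or log-link regression with robust standard errors. The log-link form also yields the ratio in which section 1.8 states the expected effect; it is an option, not a requirement.
- Label the unadjusted t or Mann-Whitney test, and any further adjustment, as sensitivity analyses.

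The cost is one paragraph. Age and years of study are already collected (section 1.16). The downside is about 1-2 points of power if neither covariate predicts connections (simulated losses of 1.0-1.7 points in a log-link model at a true ratio of 1.5).
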